10.1.2 Preparation

Nivolumab Injection, 100 mg/10 mL (10 mg/mL). Nivolumab injection is to be administered as an IV infusion through a 0.2-micron to 1.2-micro pore size, low-protein binding in-line filter at the protocol-specified doses and infusion times. It is not to be administered as an IV push or bolus injection. Nivolumab injection can be infused undiluted (10 mg/mL) or diluted with 0.9% Sodium Chloride Injection, USP or 5% Dextrose Injection, USP to protein concentrations as low as 0.35 mg/mL. Total infusion volume not to exceed 120 mL. During drug product preparation and handling, vigorous mixing or shaking is to be avoided. Instructions for dilution and infusion of nivolumab injection may be provided in the clinical protocol or investigator's brochure. Care must be taken to assure sterility of the prepared solution as the product does not contain any antimicrobial preservative or bacteriostatic agent. No incompatibilities between nivolumab and polyvinyl chloride (PVC) and non-PVC/non-DEHP (di(2-ethylhexyl)phthalate) containers/IV components or glass bottles have been observed.

10.1.3 Storage and Stability

Nivolumab Injection, 100 mg/10 mL (10 mg/mL). Vials of nivolumab injection must be stored at 2° to 8°C (36° to 46°F) and protected from light and freezing.

Undiluted Nivolumab Injection and Diluted Nivolumab Injection in the IV Container. The administration of nivolumab infusion must be completed within 24 hours of preparation. If not used immediately, the infusion solution may be stored under refrigeration conditions (2° to 8°C, 36° to 46°F) for up to 24 hours, and a maximum of 8 hours of the total 24 hours can be at room temperature (20° to 25°C, 68° to 77°F) and room light. The maximum 8 hour period under room temperature and room light conditions includes the product administration period.

After final drug reconciliation, unused nivolumab vials should be disposed at the site following procedures for the disposal of anticancer drugs. Certificate of destruction for unused supply should be retained for BMS

10.1.4 Handling and Disposal

Preparation should be performed by trained personnel in accordance with good practices rules, especially with respect to asepsis.

10.1.5 Dispensing

Nivolumab must be dispensed only from official study sites and to eligible subjects under the supervision of the site investigator. Nivolumab should be stored in a secure area according to local regulations. It is the responsibility of the site investigator to ensure that study drug is only dispensed to subjects.

10.1.6 Adverse Events

Please see the current Investigator's Brochure for complete details regarding AEs of nivolumab. The most common side effects of nivolumab are:

- Fatigue
- Skin reactions: including rash, itching, hives, redness, and dry skin. Toxic epidermal necrolysis, a potentially life threatening disease characterized by blistering and peeling of the top layer of skin resembling that of a severe burn, has occurred in one subject who received ipilimumab after nivolumab treatment.
- Diarrhea
- Nausea
- Abdominal pain
- Decreased appetite
- Low red blood cells
- Fever
- Joint pain or stiffness

10.2 Ipilimumab

Ipilimumab is a recombinant, human monoclonal antibody that binds to the CTLA-4. Ipilimumab is an IgG1 kappa immunoglobulin with an approximate molecular weight of 148 kDa.

Ipilimumab is produced in mammalian (Chinese hamster ovary) cell culture.

Bristol-Myers Squibb (BMS) will supply ipilimumab. Ordering of ipilimumab will take place through the BMS vendor.

10.2.1 Pharmacokinetics (PK)

Ipilimumab as a single agent: The pharmacokinetics of ipilimumab was studied in 499 subjects with unresectable or metastatic melanoma who received doses of 0.3, 3, or 10 mg/kg administered once every 3 weeks for four doses. Peak concentration (Cmax), trough concentration (Cmin), and area under the curve (AUC) of ipilimumab were found to be dose proportional within the dose range examined. Upon repeated dosing of ipilimumab administered every 3 weeks, ipilimumab clearance was found to be time invariant, and minimal systemic accumulation was observed as evident by an accumulation index of 1.5-fold or less. Ipilimumab steady-state concentration was reached by the third dose. The following mean (percent coefficient of variation) parameters were generated through population PK analysis: terminal half-life of 14.7 days (30.1%); systemic clearance (CL) of 15.3 mL/h (38.5%); and volume of distribution at steady-state (Vss) of 7.21 L (10.5%). The mean (\pm SD) ipilimumab Cmin achieved at steady-state with the 3-mg/kg regimen was 21.8 mcg/mL (\pm 11.2).

Nivolumab in combination with ipilimumab: The geometric mean (%CV) CL, Vss, and terminal half-life of nivolumab were 10.0 mL/h (50.3%), 7.92 L (30.1%), and 24.8 days (94.3%), respectively. When administered in combination, the CL of nivolumab was increased by 24%, whereas there was no effect on the clearance of ipilimumab. When administered in combination, the clearance of nivolumab increased by 42% in the presence of anti-nivolumab antibodies. There was no effect of anti-ipilimumab antibodies on the clearance of ipilimumab.

Specific Populations: Cross-study analyses were performed on data from subjects with a variety of conditions, including 420 subjects with melanoma who received single or multiple infusions of ipilimumab at doses of 0.3, 3, or 10 mg/kg. The effects of various covariates on ipilimumab PKs were assessed in population pharmacokinetic analyses.

Ipilimumab CL increased with increasing body weight; however, no dose adjustment of Ipilimumab is required for body weight after administration on a mg/kg basis. The following factors had no clinically meaningful effect on the CL of ipilimumab: age (range 26 to 86 years), gender, concomitant use of budesonide, performance status, HLA-A2*0201 status, positive anti-ipilimumab antibody status, prior use of systemic anticancer therapy, or baseline lactate dehydrogenase (LDH) levels. The effect of race was not examined as there were insufficient numbers of subjects in non-Caucasian ethnic groups.

Renal Impairment: Creatinine clearance at baseline did not have a clinically important effect on ipilimumab pharmacokinetics in subjects with calculated creatinine clearance values of 29 mL/min or greater.

Hepatic Impairment: Baseline AST, total bilirubin, and ALT levels did not have a clinically important effect on ipilimumab pharmacokinetics in subjects with various degrees of hepatic impairment.

10.2.2 Preparation

Ipilimumab is a sterile, preservative-free, clear to slightly opalescent, colorless to pale yellow solution for intravenous infusion, which may contain a small amount of visible translucent-to-white, amorphous ipilimumab particulates. It is supplied in single-use vials of 200 mg/40 mL. Each milliliter contains 5 mg of ipilimumab and the following inactive ingredients: diethylene triamine penta acetic acid (DTPA) (0.04 mg), mannitol (10 mg), polysorbate 80 (vegetable origin) (0.1 mg), sodium chloride (5.85 mg), tris hydrochloride (3.15 mg), and Water for Injection, USP at a pH of 7.

Do not shake product.

Inspect parenteral drug products visually for particulate matter and discoloration prior to administration. Discard vial if solution is cloudy, there is pronounced discoloration (solution may have pale yellow color), or there is foreign particulate matter other than translucent-to white, amorphous particles.

Preparation of Solution:

- Allow the vials to stand at room temperature for approximately 5 minutes prior to preparation of infusion.
- Withdraw the required volume of ipilimumab and transfer into an intravenous bag.
- Dilute with 0.9% Sodium Chloride Injection, USP or 5% Dextrose Injection, USP to prepare a diluted solution with a final concentration ranging from 1 mg/mL to 2 mg/mL. Mix diluted solution by gentle inversion.
- Store the diluted solution for no more than 24 hours under refrigeration (2°C to 8°C, 36°F to 46°F) or at room temperature (20°C to 25°C, 68°F to 77°F).
- Discard partially used vials or empty vials of ipilimumab.

10.2.3 Storage and Stability

Store ipilimumab under refrigeration at 2°C to 8°C (36°F to 46°F). Do not freeze. Protect vials from light.

10.2.4 Administration

Do not mix ipilimumab with, or administer as an infusion with, other medicinal products. Flush the intravenous line with 0.9% Sodium Chloride Injection, USP or 0.5% Dextrose Injection, USP after each dose. Administer diluted solution over 30 minutes (+/- 10 minutes) through an intravenous line containing a sterile, non-pyrogenic, low-protein-binding in-line filter.

10.2.5 Handling and Disposal

Accountability for investigational product is the responsibility of the investigator. The research pharmacy will maintain a careful record of the inventory and disposition of the agent using the NCI Drug Accountability Record Form (DARF) or another comparable drug accountability form.

Qualified personnel, familiar with procedures that minimize undue exposure to themselves and the environment, should undertake the preparation, handling, and safe disposal of the chemotherapeutic agent in a self-contained and protective environment.

Drug should be destroyed at the site, after the investigator approves the drug destruction policy at the site. Drug will not be returned to BMS. Destruction will be documented in the Drug Accountability Record Form and certificate of destruction provided to BMS.

10.2.6 Compatibility

No incompatibilities between the nivolumab and ipilimumab have been observed. When both study drugs are to be administered on the same day, separate infusion bags and filters must be used for each infusion. Nivolumab is to be administered first. The nivolumab infusion must be promptly followed by a saline flush to clear the line of nivolumab before starting the ipilimumab infusion. The second infusion will always be ipilimumab, and will start at least 30 minutes after completion of the nivolumab infusion.

Ipilimumab may be diluted in 0.9% Sodium Chloride Solution or 5% Dextrose solution.

Nivolumab may be diluted in 0.9% Sodium Chloride Solution.

10.2.7 Adverse Events

Based on data from the Phase I study, nivolumab in combination with ipilimumab has an acceptable safety profile in RCC. In summary, AEs were reported in 97.7% of subjects treated with nivolumab in combination with ipilimumab. The most frequently reported drug-related AEs in subjects treated with 3-mg/kg nivolumab + 1-mg/kg ipilimumab included fatigue (11 subjects, 52.4%), rash (8 subjects, 38.1%), diarrhea (6 subjects, 28.6%), and pruritus (6 subjects, 28.6%); the majority were Grade 1-2. The most frequently reported drug-related AEs in subjects treated with 1-mg/kg nivolumab + 3-mg/kg ipilimumab included fatigue (16 subjects, 69.6%); nausea, ALT increased, AST increased (9 subjects each, 39.1%); and diarrhea (8 subjects, 34.8%). The majority were Grade 1-2. The majority of deaths were due to disease progression. No drug-

related deaths have been reported to date. Please refer to the most current IB for a comprehensive list of AEs.

11. ADVERSE EVENTS

The descriptions and grading scales found in the NCI CTCAE v4.03 will be utilized for AE assessment throughout the life of the protocol. A copy of the CTCAE v4.03 criteria can be downloaded from the CTEP website at <http://ctep.cancer.gov>. All forms for AE/SAE recording and reporting can be found in the Study Procedure Manual or in the EDC system (Documents and Information Tab).

11.1 Definitions

11.1.1 Adverse Event (AE)

An AE is any untoward medical occurrence whether or not considered related to the study drug that appears to change in intensity during the course of the study. The following are examples of AEs:

- Unintended or unfavorable sign or symptom
- A disease temporally associated with participation in the protocol
- An intercurrent illness or injury that impairs the well-being of the subject

Abnormal laboratory values or diagnostic test results constitute AEs only if they induce clinical signs or symptoms or require treatment or further diagnostic tests

Hospitalization for elective surgery or routine clinical procedures that are not the result of an AE (e.g., surgical insertion of central line) should not be recorded as an AE.

Disease progression should not be recorded as an AE, unless it is attributable to the study regimen by the site investigator.

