1.4 Nivolumab in RCC

A first-in-human Phase I study of nivolumab was performed in patients with treatment refractory solid tumors [16]. Nivolumab was administered as a single dose ranging from 0.3 to 10mg/kg and objective responses were noted including in a patient with RCC and there were no dose limiting toxicities observed within 4 weeks of the initial dose. The serum half-life of nivolumab ranged from 12 to 20 days. A multi-dose Phase I dose escalation trial extended the above findings in 296 patients with advanced solid tumors given nivolumab at doses from 0.1 to 10 mg/kg every 2 weeks for up to 2 years [17]. Objective tumor responses were noted in 9 of 33 patients with RCC. Common treatment related side effects were fatigue, anorexia, nausea, rash, and diarrhea. Grade 3 or 4 toxicities were reported in 14% of patients and evident at all dose levels without obvious dose dependency but only 15 patients (5%) discontinued treatment for toxicity reasons. Immune related adverse events of special interest were observed including pneumonitis, colitis, hepatitis, hypophysitis and thyroiditis but were reversible. Extended follow up of patients on this study showed a median response duration of 12.9 months and median overall survival in this heavily pretreated population was 22.4 months [18]. Three of 5 patients who stopped treatment while responding continued to respond for at least 45 weeks. Among 168 RCC patients randomized in blinded fashion to nivolumab dosed at 0.3, 2 and 10mg/kg, there was no observable dose-response relationship with objective responses in 20-22% of patients and

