1.5 Nivolumab + Ipilimumab in RCC

The combination of nivolumab and ipilimumab has been extensively tested in patients with metastatic melanoma and found to have superior clinical outcomes to ipilimumab and likely nivolumab alone but at the cost of a higher frequency of serious adverse events [22, 23]. In a Phase I trial (CheckMate 016) patients with advanced RCC were randomized to receive nivolumab 3 mg/kg plus ipilimumab 1 mg/kg (N3 + I1, 47 patients) or nivolumab 1 mg/kg plus ipilimumab 3 mg/kg (N1 + I3, 47 patients) intravenously every 3 weeks for 4 doses followed by nivolumab every 2 weeks [24]. An exploratory nivolumab 3 mg/kg plus ipilimumab 3 mg/kg arm (N3 + I3) showed unacceptable early toxicity after 6 patients and did not proceed to the expansion phase. Approximately half the patients were previously treated. Treatment-related toxicities were seen in 88% of patients and 16% discontinued therapy for toxicity reasons. Serious Grade 3 or 4 treatment-related adverse events occurred in 34% and 64% of patients in N3 + I1 and N1 + I3, respectively, most commonly manifest as elevated lipase or amylase, elevated liver function tests, diarrhea and colitis. After a median 8 months of follow up, the objective response rate was 38% and 43% and median progression free survival was 30.3 and 36 weeks respectively in N3 + I1 and N1 + I3 arms. Among responders, the median duration of response was 67.7 weeks (range 4.1+ to 91.1+) in the N3 + I1 arm and 81.1 weeks (range 6.1+ to 81.1+) in the N1 + I3 arm. Overall both treatment arms appeared to confer similar anti-tumor activity but the N1 + I3 arm was associated with higher gastrointestinal and hepatic toxicities. The promising activity and tolerability of the N3 + I1 schedule has led to an ongoing randomized Phase III registration trial comparing this combination to sunitinib monotherapy in the approved schedule, in patients with advanced clear cell RCC. This trial reached its accrual goal of 1070 patients in the fall of 2015. The co-primary endpoints are progression free and overall

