2.2.2 Secondary Endpoints

- Apply the PRP model, developed in the DF/HCC Kidney SPORE Project 4, to assign each patient a probability of having PFS > 1 year.
- The endpoint for Part B (addition of ipilimumab) will be objective response (CR or PR) taking as baseline tumor measurements at the patient's start of Part B.
- An expected cohort of 40 nccRCC patients will be enrolled in the trial and analyzed separately for evidence of anti-tumor activity, principally focusing on objective response rate (CR or PR).
- Toxicity by CTCAE criteria of nivolumab monotherapy in treatment naïve patients with cc and nccRCC.

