6. TOXICITIES AND DOSE DELAYS

The NCI Common Terminology Criteria for Adverse Events (CTCAE) v4.03 will be used to grade adverse events.

Subjects enrolled in this study will be evaluated clinically and with standard laboratory tests before and at regular intervals during their participation in this study as specified in Study Calendar & Evaluations.

Subjects will be evaluated for adverse events (all grades), serious adverse events, and adverse events requiring study drug interruption or discontinuation as specified in Study Calendar & Evaluations.

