6.1.1 Dose Delay Criteria

Dose delay criteria apply for all drug-related adverse events (regardless of whether or not the event is attributed to nivolumab, ipilimumab or both). Study drugs (both agents if on induction phase of Part B) must be held/omitted until treatment can resume. Please see Appendix A for AE management guidelines.

Nivolumab and ipilimumab administration should be omitted for the following:

- Any Grade ≥ 2 non-skin, drug-related adverse event, with the following exceptions:
 - Grade 2 drug-related fatigue or laboratory abnormalities that do not require a treatment delay (with the exception of Grade 3 AST, ALT or total bilirubin in patients with normal baseline values-see below).
- Any Grade 3 skin, drug-related adverse event
- Any Grade 3 drug-related laboratory abnormality, with the following exceptions:
 - Grade 3 amylase or lipase abnormalities that are not associated with symptoms or clinical manifestations of pancreatitis do not require a dose delay. It is recommended to consult with the principal investigator for Grade 3 amylase or lipase abnormalities.
 - If a subject has a baseline AST, ALT, or total bilirubin that is within normal limits, delay dosing for drug-related Grade ≥ 2 toxicity
 - If a subject has baseline AST, ALT, or total bilirubin within the Grade 1 toxicity range, delay dosing for drug-related Grade ≥ 3 toxicity
- Any adverse event, laboratory abnormality, or intercurrent illness which, in the judgment of the site investigator, warrants delaying the dose of study medication.

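### Section 11.1.1 may leave some symptom-free Grade 3 or higher laboratory values, chiefly Grade 3 amylase or lipase, out of the toxicity count, depending on whether a site re-tests

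*Combined protocol and SAP*

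**What the plan says.** Section 11.1.1 sets the rule for laboratory findings: "Abnormal laboratory values or diagnostic test results constitute AEs only if they induce clinical signs or symptoms or require treatment or further diagnostic tests". A finding can therefore qualify without symptoms, but only through treatment or further testing. A withheld dose is not one of the qualifying conditions.

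The rest of the safety plan is built on CTCAE grades:

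- Section 11 opens with: "The descriptions and grading scales found in the NCI CTCAE v4.03 will be utilized for AE assessment throughout the life of the protocol".
- A secondary endpoint (2.2.2, repeated in 12.7.2) is: "Toxicity by CTCAE criteria of nivolumab monotherapy in treatment naïve patients with cc and nccRCC".
- Section 6 states: "Subjects will be evaluated for adverse events (all grades), serious adverse events, and adverse events requiring study drug interruption or discontinuation".
- Section 12.9 assesses safety by CTCAE v4.03 in everyone given at least one dose, with Part B handled separately. It adds immune-related events but no analysis of graded laboratory values.

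Section 6.1.1 adds this exemption: "Grade 3 amylase or lipase abnormalities that are not associated with symptoms or clinical manifestations of pancreatitis do not require a dose delay". For such findings it recommends consulting the principal investigator. It does not ask for a repeat test.

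The study calendar (footnote 3) schedules amylase, lipase, LDH, uric acid and CPK on Day 1 of every cycle.

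**The concern.** The protocol assigns grades to laboratory values whether or not the patient has symptoms; the amylase and lipase exemption in 6.1.1 is worded that way. Under 11.1.1, however, a value can be Grade 3 and still not be an adverse event. Where nothing obliges a site to act on the value, recording depends on habit: a site that repeats the test has an adverse event to enter, and a site that waits for the next scheduled draw does not.

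At stake is the Grade 3-4 rate, the figure most readers will take from the safety results. Compared with a count of all graded values, the rule can only lower that rate, and the shortfall could differ between sites. The monitoring committee's listed safety item is an adverse event summary report (Section 13.2), so the same values could be missing there.

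**Working it through.** No sample size, power figure or decision threshold depends on the adverse event definition, and the plan states no figure to reproduce. The check is mainly textual.

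**Step 1. Which symptom-free findings can escape 11.1.1?**

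| Finding, no symptoms | What the protocol says follows | Adverse event under 11.1.1? |
|---|---|---|
| Grade 3 amylase or lipase | No delay; consultation recommended (6.1.1). In Part B Cycles 1-2, extra testing after abnormal results is encouraged, at the site investigator's discretion (calendar footnote 10) | Only if the site treats or re-tests |
| Grade 4 amylase or lipase | Exempt from discontinuation in terms of a fall below Grade 4 within 2 weeks, or a fall held for 1 week after immunosuppression stops (6.1.3) | Very likely yes: scheduled draws come once per 6- or 12-week cycle, so the first condition needs an extra test, and the second involves treatment |
| Grade 3 or higher AST, ALT or bilirubin | Delay (6.1.1), resumption tied to recovery (6.1.2), search for other causes and possible imaging (Appendix A) | Mostly yes, through further tests |

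The first row is the clear gap.

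**Step 2. Does Section 6 agree with 11.1.1?** In 6.1.1, laboratory abnormalities that need no delay appear as an exception to a rule about Grade 2 or higher drug-related adverse events. In 6.1.3, drug-related laboratory abnormalities are an exception to a rule about Grade 3 drug-related adverse events. An exception makes sense only if the item belongs to the class, so both treat these findings as adverse events. Elsewhere, including the Grade 4 rule in 6.1.3, the two are named as alternatives. Section 6 is thus not uniform, and in the first two places it conflicts with 11.1.1.

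**Step 3. Which cited data bear on this?**

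- Combination (Section 1.5): "Serious Grade 3 or 4 treatment-related adverse events occurred in 34% and 64% of patients in N3 + I1 and N1 + I3, respectively", with the events "most commonly manifest as elevated lipase or amylase, elevated liver function tests, diarrhea and colitis". The list gives no counts and no symptom status. N3 + I1 matches the Part B induction doses; N1 + I3 does not.
- Combination (Section 10.2.7): ALT and AST increases are reported as drug-related adverse events in 9 subjects each (39.1%) under N1 + I3. The N3 + I1 list there has no laboratory term.
- Monotherapy (Section 1.4): "Grade 3 or 4 toxicities were reported in 14% of patients" in the multi-dose Phase I trial, and 19% in the Phase III trial. Neither rate is broken down by event type, and the common effects named for the Phase I trial are all clinical.

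**Step 4. Size.** Let f be the share of patients with any Grade 3-4 event whose only such event is an unrecorded laboratory value. Then

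recorded rate = true rate × (1 − f).

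The share must be of patients, not events: someone with an unrecorded lipase rise and recorded Grade 3 colitis still counts. The documents do not give f. To show the mechanics only, take 34% as the true Part B rate and 60 patients:

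- f = 0: 34% × 1 = 34%, or 0.34 × 60 = 20.4 patients; no understatement.
- f = 0.10 (assumed): 34% × 0.90 = 30.6%, or 0.306 × 60 = 18.4 patients; about 2 fewer.

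Nothing in the documents supports choosing one value of f over another. The 34% is itself a loose stand-in, since Part B patients have already had nivolumab and those with non-endocrine Grade 3 toxicity on it are excluded.

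**The case against.** The strongest reply is that the gap is narrow. Section 11.1.1 keeps any value that needs treatment or further tests, which captures most severe liver test rises and, in practice, Grade 4 amylase or lipase. In Part B induction, where the combination is given, footnote 10 encourages extra testing after abnormal results. Most patients with a severe laboratory value might be counted anyway, some through another severe event. Section 12 also sets no toxicity hypothesis or historical comparison that the definition could upset. All of this stands, and it limits the size. It does not remove the gap for symptom-free Grade 3 amylase or lipase: the extra testing is discretionary, and outside those two cycles it is not mentioned for these enzymes.

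A reader might infer more than the documents support:

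- *That symptom-free laboratory abnormalities are left out as a class.* They are not; the treatment and further-test routes remain.
- *That the monotherapy toxicity endpoint is shown to be understated.* The laboratory evidence comes from the combination trial, and the 14% and 19% monotherapy rates have no breakdown.
- *That laboratory rises are the leading severe toxicity.* The list in Section 1.5 also names diarrhea and colitis, without counts.
- *That the results could not be compared with the cited rates.* The adverse event definitions in those studies are not given, so this is plausible but not shown.
- *That the recording rule changes who enters Part B.* Sections 3.3, 5 and 5.2 refer to Grade 3 toxicity or Grade 3 or higher immune-related events, and nothing ties these to the 11.1.1 count.

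**Conclusion.** The concern holds in a limited form. Read as written, 11.1.1 allows some symptom-free Grade 3 or higher laboratory values to go unrecorded as adverse events, most clearly Grade 3 amylase or lipase, according to whether a site re-tests. This conflicts with parts of Section 6 and sits badly with a safety analysis based on CTCAE grades, and no planned table makes up for it. Any bias is downward. Its size is unknown and may be near zero. The case is strongest for the separate Part B safety analysis; for Part A the same rule applies, but the documents give no evidence on how often it would matter.

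This rests on two assumptions: that sites follow 11.1.1 literally, and that a routine draw at the next cycle does not count as a further diagnostic test.

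**What to change.** In Section 12.9, add a table of the worst treatment-emergent CTCAE v4.03 grade per patient for each scheduled laboratory test, separately for Parts A and B. Report the proportion of patients with any Grade 3 or higher toxicity twice: with and without those whose only such finding is a laboratory value. Because the table is built from the values themselves, it does not depend on whether a site entered an adverse event.

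Reconcile 11.1.1 with Sections 6.1.1 and 6.1.3, so that the protocol says in one place whether a graded laboratory abnormality without symptoms is an adverse event. State that the change is for reporting only and leaves SAE reporting, dosing rules and Part B eligibility as they are.

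The tests are already on the calendar, so no new procedure is needed. The cost is one wording change, some extra tabulation and a possibly higher reported Grade 3-4 rate. Showing both rates lets readers see how much of any increase is laboratory-only.
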